## 6.3.2 Maximal Exercise Testing Laboratory Parameters

The following serial laboratory parameters are assessed at resting, at peak work, 5 minutes after reaching peak work, and 10 minutes after reaching peak work. The MMRM analysis should incorporate the visit and time (during the exercise test) interaction for maximal exercise testing laboratory parameters, as described in Section 6.3.

Table 3: Laboratory Parameters Collected During Maximal Exercise Testing	Table 3: Laborator	v Parameters	Collected	During N	Maximal E	Exercise [	Festing
--	--------------------	--------------	-----------	----------	------------------	------------	----------------

	At Rest	At Maximal	5 min	10 min
Parameter	(Prior to	Work (End	After End	After End
	Test)	of Test)	of Test	of Test
Blood Glucose ( mg/dL )	X	X	X	X
Blood Lactate ( mM )	X	X	X	X
Blood Pyruvate ( mM )	X	X	X	X
Blood Potassium ( mM/L )	X	X	X	X

Observed values and difference between resting and 0, 5, or 10 minutes after peak performance for these parameters will be summarized at baseline and at each timepoint. For parameters measured at resting and 0, 5, or 10 minutes after the end of the maximal exercise test, the change from resting and the change from baseline should be calculated.

The change from resting (delta) for parameters measured at resting and 10 min after the end of the maximal exercise test is defined as:

Delta = [Parameter at 0, 5, or 10 min after end of exercise testing] - [Parameter at resting]

The change from baseline is defined for parameters measured at resting and 0, 5, or 10 min after the end of the maximal exercise test is defined as:

Change from Baseline in Delta= [Parameter at Y min after end of exercise testing(At Visit X) - Parameter at resting(At Visit X)] - [Parameter at Y min after end of exercise testing(At Baseline) - Parameter at resting(At Baseline)]

Summary statistics at resting, at the completion of the maximal exercise test, 5 minutes after exercise test, and 10 minutes after exercise test will be provided.

#### 6.3.3 Submaximal Exercise Testing Parameters

The following parameters are assessed at resting, at 10 minutes, 20 minutes, and 30 minutes during the submaximal exercise test.

Table 4: Submaximal Exercise Testing Parameters

Parameter	At Rest (Prior to Test)	10 minutes	20 minutes	30 minutes (End of Test)
Borg		X	X	X
Leg Effort Rating of Perceived Exertion		X	X	X
Heart Rate ( bpm ) a	X	X	X	X
Carbon Dioxide Production (VCO 2 ) ( mL/kg/min ) a,b	X	X	X	X
Oxygen Comsumption (VO 2 ) ( mL/kg/min ) a,b	X	X	X	X
Expired Air Gas Volume (VeBTPS) ( L/min ) a	X			X
Cardiac Output ( L/min ) a	X			X
Arteriovenous Oxygen Difference (a-VO 2diff ) ( mLO2/dlQ ) a	X			X
Respiratory Exchange Ratio a	X			X
Starting Workload ( W )	X			
Exercise Duration ( min )				X
Final Workload ( W )				X

<sup>aObserved values and difference between resting and 30 minutes for these parameters will be summarized at baseline and at each timepoint. For parameters measured at resting and at the end of the submaximal exercise test (for patients who complete 30 minutes of the test), the change from resting and the change from baseline should be calculated.

The change from resting (delta) for parameters measured at resting and at the end of the submaximal exercise test is defined as:

Delta = Parameter at 10, 20, or 30 min - Parameter at resting

The change from baseline is defined for parameters measured at resting and at the end of the submaximal exercise test is defined as:

Change from baseline in Delta= [Parameter at Y min (At Visit X) - Parameter at resting(At Visit X)] - [Parameter at Y min (At Baseline) - Parameter at resting(At Baseline)]

Summary statistics at resting, at 10 minutes, 20 minutes, and 30 minutes will be provided.

b Analysis of VO2 and VCO2 will be performed using adjustments for weight at the visit week in which the submaximal exercise test was performed

The MMRM analysis should incorporate the visit and time (during the exercise test) interaction for change from baseline heart rate, as described in Section 6.3.

The change from baseline resting heart rate is defined as:

Change from baseline in Heart Rate= [Heart Rate at Y min (At Visit X) - Heart Rate at resting(At Visit X)] - [Heart Rate at Y min (At Baseline) - Heart Rate at resting(At Baseline)]

Analysis visits 0, 4, 8 and 12 will be used. The pairwise dose group comparisons with placebo will be estimated using the difference in adjusted means and 95% CI for the difference in changes from baseline to Week 12.

#### 6.3.4 Submaximal Exercise Testing Laboratory Parameters

The following laboratory parameters are assessed at resting, at 10 minutes, 20 minutes, and 30 minutes during the submaximal exercise test.

Parameter	At Rest (Prior to Test)	10 minutes	20 minutes	30 minutes (End of Test)
Blood Glucose ( mg/dL ) a	X	X	X	X
Blood Lactate ( mM ) a	X	X	X	X
Blood Pyruvate ( mM )a	X	X	X	X

aObserved values and difference between resting and 30 minutes for these parameters will be summarized at baseline and at each timepoint. For parameters measured at resting and at the end of the submaximal exercise test (for patients who complete 30 minutes of the test), the change from resting and the change from baseline should be calculated.

The change from resting (delta) for parameters measured at resting and at the end of the submaximal exercise test is defined as:

Delta = Parameter at 10, 20, or 30 min - Parameter at resting

The change from baseline is defined for parameters measured at resting and at the end of the submaximal exercise test is defined as:

Change from baseline in Delta= [Parameter at Y min (At Visit X) - Parameter at resting(At Visit X)] - [Parameter at Y min (At Baseline) - Parameter at resting(At Baseline)]

Summary statistics at resting, at 10 minutes, 20 minutes, and 30 minutes will be provided.

The MMRM analysis of change from baseline blood lactate should incorporate the visit and time (during the exercise test) interaction for submaximal exercise testing laboratory parameters, as described in Section 6.3.

The change from resting blood lactate is defined as:

 Change from baseline in Blood Lactate= [Blood Lactate at Y min (At Visit X) - Blood Lactate at resting(At Visit X)] - [Blood Lactate at Y min (At Baseline) - Blood Lactate at resting(At Baseline)] Analysis visits 0, 4, 8 and 12 will be used. The pairwise dose group comparisons with placebo will be estimated using the difference in adjusted means and 95% CI for the difference in changes from baseline to Week 12.

Page 28 of 38

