### **11.2.** Submaximal Exercise Test

The following parameters will be collected during the submaximal exercise test and analyzed from Baseline to Weeks 4 and 12: change in peak serum lactate, change in peak serum pyruvate, change in peak heart rate, and change in the rating of perceived exertion.

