## 2.3.1 Efficacy Endpoints

The primary efficacy endpoint is change in peak work. Peak work will be derived by dividing the maximum work load (watts) at each visit by the patient's baseline weight (kg). Peak work will be rounded to the 0.0001 digit.

The secondary efficacy endpoint is the change in 6-minute walk test (6MWT) distance.

Exploratory endpoints for this trial include:

- To evaluate the change in peak oxygen utilization during maximal exercise testing
- To evaluate the change in peak blood lactate and pyruvate, peak heart rate, and rating of perceived exertion during submaximal exercise testing
- To evaluate the change in Fatigue Severity Scale score
- To evaluate the change in SF-36® Health Survey Update (SF-36) score
- Parameters assessed from blood lactate and serum pyruvate during submaximal exercise testing

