# 2.4 Changes from Protocol-Specified Analysis

There are no planned changes to analyses from what is described in the protocol.

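### The SAP names change in peak submaximal lactate, pyruvate and heart rate but defines no submaximal peak; its detailed lactate and heart-rate models use a rest-subtracted difference, which is another quantity

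*SAP*

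**What the plan says.** **Endpoint.** Protocol 11.2 lists "change in peak serum lactate, change in peak serum pyruvate, change in peak heart rate, and change in the rating of perceived exertion", from Baseline to Weeks 4 and 12. SAP 2.3.1 repeats it with blood in place of serum: "To evaluate the change in peak blood lactate and pyruvate, peak heart rate, and rating of perceived exertion during submaximal exercise testing". Protocol 6.3 and SAP 1.1.3 carry the same objective. SAP 2.3.1 also has a separate, looser entry: "Parameters assessed from blood lactate and serum pyruvate during submaximal exercise testing".

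**Modelled variable.** SAP 6.3.4 defines, for lactate, "Change from baseline in Blood Lactate= [Blood Lactate at Y min (At Visit X) - Blood Lactate at resting(At Visit X"; once the bracket closes, the same difference at baseline is subtracted. SAP 6.3.3 has the matching form for heart rate: "Change from baseline in Heart Rate= [Heart Rate at Y min (At Visit X) - Heart Rate at resting(At Visit X", again less its baseline counterpart. The times are 10, 20 and 30 minutes. SAP 6.3 fits these in a treatment by time by week model, adding baseline resting lactate as a covariate for lactate.

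**Departures.** SAP 2.4 states: "There are no planned changes to analyses from what is described in the protocol".

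**The concern.** A programmer working from SAP 6.3.3 and 6.3.4 has a full formula for the rise above rest and none for the peak. Nothing visible says whether the submaximal peak is the highest sample or the 30-minute value, or what to do when a patient stops early. Footnotes in both sections limit end-of-test change calculations to patients who complete 30 minutes, so early stopping is foreseen but not resolved for a peak.

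The labels add to the difficulty. The same double difference is called a change from baseline in delta (6.3, 6.3.3, 6.3.4), a change from baseline in heart rate and a change from baseline resting heart rate (both in 6.3.3), and a change from baseline in blood lactate and a change from resting blood lactate (both in 6.3.4). A reader of an output table could take it for a change in level or in peak.

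At stake is how the submaximal results are read. Pharmacodynamic data are one of several inputs to choosing the Part 2 doses (Protocol 7.1, 7.4.1). SAP 3.4 names subgroups by resting lactate and resting heart rate, so resting values matter to the sponsor, and these are the values the formula nets out.

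**Working it through.** The documents give no power, alpha or expected effect for this endpoint, so there is no stated figure to reproduce. The check is the algebra of the SAP formula, followed by assumed values.

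**Identity.** Let baseline be R0 at rest and Y0 at time Y. Let the visit values be R0 + r and Y0 + x.

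- SAP quantity: [(Y0 + x) - (R0 + r)] - [Y0 - R0] = x - r.
- Change in the exercise value at that time: x. This is also the change in peak when the peak falls at that time on both occasions.

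For active (A) against placebo (P) at a fixed time, the contrast is (xA - rA) - (xP - rP) = (xA - xP) - (rA - rP). A resting shift common to both arms cancels; a treatment effect on rest does not, and it enters with the opposite sign.

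**Assumed lactate profiles** (mM, at rest/10/20/30 min; illustrative, not from the documents):

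| Case | Baseline | Visit | Change in peak | Change at rest | SAP quantity at 10/20/30 min |
|---|---|---|---|---|---|
| A. Equal fall everywhere | 2/5/6/6 | 1.5/4.5/5.5/5.5 | -0.5 | -0.5 | 0/0/0 |
| B. Only rest falls | 2/5/6/6 | 1.5/5/6/6 | 0 | -0.5 | +0.5/+0.5/+0.5 |
| C. Only exercise values fall | 2/5/6/6 | 2/4.5/5.5/5.5 | -0.5 | 0 | -0.5/-0.5/-0.5 |
| D. Peak moves from 10 to 30 min | 2/6/5/4.5 | 2/4.5/5/6 | 0 | 0 | -1.5/0/+1.5 |

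Case A at 30 minutes: (5.5 - 1.5) - (6 - 2) = 4 - 4 = 0, against a peak change of 5.5 - 6 = -0.5. Case D shows that timing alone separates the two quantities even when rest is stable.

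**Range.** For a peak fall of 1.0 mM at a fixed time, the SAP quantity is -1.0 - r:

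- r = 0 gives -1.0
- r = -0.25 gives -0.75
- r = -0.5 gives -0.5
- r = -1.0 gives 0

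**Covariate.** Baseline resting lactate adjusts for R0. It does not restore r, the on-treatment change at rest, so it does not turn x - r into x.

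**The case against.** Much of the case on the other side stands.

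- **A reader might infer that the peak endpoint has been dropped.** The documents do not support that. SAP 6.3 promises summary statistics and MMRM treatment differences in change from baseline for every exploratory endpoint unless otherwise noted, and the peak endpoint is on that list. What is missing is the operational definition.
- **A reader might infer that an equal fall at rest and exercise would be reported as no effect.** The model would show none, but SAP 6 calls for observed values and changes from baseline by group, and 6.3.3 and 6.3.4 call for summaries at rest, 10, 20 and 30 minutes. The fall would be visible descriptively.
- **Sections are missing from the public SAP.** The text passes from 7.8 to 10. A pharmacodynamic section there could define a lactate or pyruvate peak, so the absence can be stated only for the visible text.
- **The rest-subtracted analysis is legitimate.** It can serve the separate lactate-parameters entry in SAP 2.3.1.
- **Dose choice does not hang on this table.** Protocol 7.1 and SAP 1.2 base it on available safety, efficacy, PK and PD data together.
- **No resting effect is documented.** If rest is stable and the peak time fixed, the two quantities agree, as in case C.

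What does not stand is that the general promise in SAP 6.3 closes the gap. It supplies no peak variable, and for measurements repeated within a test the same section directs the time-by-week model, whose response 6.3.3 and 6.3.4 define for heart rate and lactate as the double difference. Printing the formula beside each label shows the programmer what to compute, but does not make it the named endpoint.

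**Conclusion.** Wrong as written, in a limited way. The endpoint named in both documents is change in peak; the response defined in detail for lactate and heart rate is change in the exercise-induced rise. The two differ by the resting change r and by any shift in the time of the peak. Pyruvate shares the missing peak definition, although 6.3.4 spells out the model response only for lactate. SAP 2.4 should not declare that nothing has changed while this stands, particularly since SAP Section 1 makes the SAP govern where it and the protocol differ.

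The size in practice is unknown: the mM figures are assumptions, and the gap ranges from nothing (stable rest, fixed peak time) to the whole effect (rest and exercise values move together). The endpoint is exploratory, its p-values are descriptive only, and the peak-work analysis is unaffected. The finding rests on the visible SAP text.

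**What to change.** In SAP 6.3.3 and 6.3.4:

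1. Define the submaximal peak at each visit for lactate, pyruvate and heart rate, for example as the maximum over the scheduled exercise samples. State a rule for tests stopped before 30 minutes, such as comparing only time points available at both visits, so that maxima over different numbers of samples are not set against each other.
2. Analyse change from baseline in that peak at Weeks 4 and 12, each dose against pooled placebo. Baseline peak as a covariate is optional, given the small cohorts.
3. Keep the double difference as a supportive analysis under one label throughout, such as change from baseline in delta (exercise minus rest), with the change in the resting value shown beside it.

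Alternatively, restate the endpoint as change in exercise-induced rise and record the departure in SAP 2.4.

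The first route needs SAP wording and one derived variable per parameter from samples already collected; its cost is a few extra exploratory tables. The second needs wording only, but gives up the endpoint the protocol names.

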#### 7. SAFETY ANALYSIS

Safety and tolerability are evaluated by AEs, SAEs, clinical laboratory test results, body weight, vital sign, 12-lead electrocardiogram [ECG], echocardiogram, and physical examination assessments. All analyses of the safety data will be performed using the safety analysis set. Descriptive statistics (described in Section 3) will be presented by treatment group assignment in the safety analysis set.

## 7.1 Adverse Events and Serious Adverse Events

All adverse event verbatim terms on eCRFs will be mapped to preferred terms and system organ classes using the Medical Dictionary for Regulatory Activities (MedDRA®) Dictionary (version 14.0). All reported AEs, SAEs, and deaths will be listed in separate patient listings.

#### 7.1.1 General Considerations for Analysis of Adverse Events

General considerations for AE summaries and calculations are:

- Multiple events by preferred term (PT) and system organ class (SOC) will be counted once
  only per patient for each treatment.
- For summaries by severity, only the most severe event will be counted per patient for each treatment.
- For summaries by relationship, only the most related event will be counted per patient for each treatment.
- An AE with a missing resolution date or incomplete date that is not identified as continuing will be assumed to be continuing and no duration will be calculated.
- AEs will be summarized by the highest dose received.
- Only treatment-emergent adverse events (TEAEs) will be included in summaries.

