### 7.4.3. Criteria for Determining Dose-Limiting Toxicity

The assessment of a DLT (i.e., a side effect serious enough to prevent an increase in dose) will be based on the clinical judgment of the investigator. Suspected DLTs should be discussed with the medical monitor. If an investigator cannot come to a firm decision whether or not to dose escalate a patient, he or she should discuss the relevant safety information with the medical monitor.

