### 7.4.4. Intra-patient Dose Escalation

Intra-patient dose escalation will only occur for the first cohort of 8 patients randomized in Part 1 of the study (i.e., those patients randomized to RTA 408 2.5 mg or placebo). Investigators, and not the DSMB, will make intra-patient dose-escalation decisions during the first cohort of Part 1. Each patient will dose escalate starting on Day 15, unless a DLT is indicated by the investigator. Patients originally randomized to RTA 408 2.5 mg will dose escalate to RTA 408 5 mg, and those randomized to placebo will remain on placebo in a blinded fashion. If the investigator cannot come to a firm decision whether or not to dose escalate a patient, he or she should discuss the relevant safety information with the medical monitor. If the investigator determines the patient should not be dose escalated, that patient should continue on their originally randomized dose (i.e., 2.5 mg or placebo) throughout the remainder of the study visits.

No other patients are eligible for intra-patient dose escalation.

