## 1.2 Part 1 Study Design

Part 1 of this study will evaluate the efficacy, safety, PK, and PD of RTA 408 in the treatment of up to approximately 64 patients with mitochondrial myopathy.

The first part of the MOTOR study will be a randomized, placebo-controlled, double-blind, dose-escalation study to evaluate the safety of RTA 408 at 2.5 mg, 5 mg, 10 mg, 20 mg and higher dose levels (not to exceed 160 mg) in up to approximately 8 cohorts of patients with mitochondrial myopathy. A cohort consists of the next eight eligible patients randomized 1:3 to placebo (n=2) or the cohort specific dose of RTA 408 (n=6). Up to 8 cohorts will be enrolled in Part 1 to allow for adequate dose-ranging for selection of RTA 408 dose(s) to be used in Part 2.

Intra-patient dose-escalation will only be utilized in the first cohort to evaluate RTA 408 at the first two dose levels (2.5 mg and 5 mg). Patients enrolling in the first cohort will be randomized to RTA 408 2.5 mg or placebo. After the Week 2 visit, each patient in the first cohort will dose escalate to 5 mg (or remain on placebo) on Day 15 unless a dose-limiting toxicity (DLT) is reported in that patient. After the last patient in the first cohort completes their Week 4 visit (i.e., 2 weeks on 2.5 mg daily [or matching placebo] followed by 2 weeks on 5 mg daily [or matching placebo]), the data safety monitoring board (DSMB) and Sponsor will review all available safety information and make a decision regarding enrollment of the next cohort. Beginning with the second 8-patient cohort, once the eighth patient enrolled completes their Week 2 visit the DSMB will review all available safety information and recommend the dose of RTA 408 for the subsequent cohort. The DSMB dose recommendation for each cohort must not exceed 100% more than the highest dose of RTA 408 evaluated in this study, and the maximum permitted dose of RTA 408 is 160 mg. The dose-level for each new cohort will not exceed the DSMB recommended dose level, and it will be selected by the Sponsor based on review of available safety, efficacy, PK, and PD data. Prior to opening each cohort in Part 1 for enrollment, the Sponsor will evaluate all available data from doses studied in Part 1 to determine if enough information is available to select doses for Part 2 of the study. Once doses are selected for Part 2 by the Sponsor, no additional cohorts will be enrolled in Part 1.

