#### 3. GENERAL CONSIDERATIONS FOR DATA ANALYSIS

#### 3.1 Analysis Considerations

All individual data will be listed as recorded in the database. All statistical summaries and analyses will be performed using SAS® software (SAS Institute, Cary, North Carolina, USA).

Only patients in the appropriate analysis set will be included in summary statistics. For endpoints discussed in this SAP, all available data for each patient will be included in summaries.

Patients randomized to RTA 408 in cohort 1 will escalate from 2.5 mg to 5 mg at Week 2. These patients will be categorized as the 5-mg treatment group for data presentations. Patients enrolled in all other cohorts will remain on their randomized dose for all 12 weeks of treatment, and will be categorized according to their randomized treatment for data presentations. Patients randomized to placebo within each cohort will be pooled for data presentations into a single placebo treatment group.

All raw patient data will be converted to SDTM for submission to FDA, however, only the analysis data will be presented in individual-patient data listings.

Continuous data will be summarized by treatment using descriptive statistics (number, mean, standard deviation [SD], minimum, median, quartiles (Q1, Q3), and maximum). Categorical data will be summarized by treatment using frequency tables (number and percentage).

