#### 3.2.1 Full Analysis Set

The full analysis set (FAS) includes all enrolled patients in Part 1, whether or not they received study drug. The FAS will be used to assess patient disposition and efficacy endpoints. Patients will be summarized according to the treatment to which they were randomized.

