## 3.2.2 Safety Analysis Set

The safety analysis set includes all patients who received at least 1 dose of study drug. The safety analysis set will be used to assess safety endpoints. Patients who receive at least 1 dose of RTA 408 will be classified in the RTA 408 group at the highest dose level received.

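### Adverse events on 2.5 mg in escalated cohort 1 patients are tabulated under 5 mg, and the SAP gives conflicting groups for a patient who never reaches 5 mg

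*SAP*

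**What the plan says.** Cohort 1 is the only cohort with escalation within a patient. SAP 1.2 and Protocol 7.4.2 start the active patients on 2.5 mg and move each one to 5 mg on Day 15 unless a DLT is reported. Whether an event is a DLT is "based on the clinical judgment of the investigator" (Protocol 7.4.3). For a patient who is not escalated, Protocol 7.4.4 says "that patient should continue on their originally randomized dose (i.e., 2.5 mg or placebo) throughout the remainder of the study visits". SAP 1.2.5 describes the escalation without the DLT exception.

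Three SAP sections then say how these patients are grouped, and a fourth applies one of the rules to adverse events:

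- 3.1, on cohort 1 patients randomised to RTA 408: "These patients will be categorized as the 5-mg treatment group for data presentations". No exception is made for patients who do not escalate.
- 3.2.1, full analysis set: "Patients will be summarized according to the treatment to which they were randomized". Cohort 1 is randomised to 2.5 mg or placebo (SAP 1.2.5).
- 3.2.2, safety set: "Patients who receive at least 1 dose of RTA 408 will be classified in the RTA 408 group at the highest dose level received". Protocol 14.3.1 has the same rule.
- 7.1.1, adverse events: "AEs will be summarized by the highest dose received".

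Treatment-emergent events count from the first dose (SAP 7.1.2). None of the summaries listed in SAP 7.1.4 is by dose at onset or by dosing period. SAP 7 presents all safety data by safety-set group.

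**The concern.** Safety is a primary objective (SAP 1.1.1), and SAP 1.2 names 2.5 mg and 5 mg as separate dose levels whose safety is to be evaluated. A reader will take the columns of a safety table as describing what happened on each dose. In cohort 1 they will not, for two reasons.

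First, an event on Day 5 in a patient who later escalates occurred on 2.5 mg but is counted under 5 mg. The same holds for laboratory results: chemistry and haematology are scheduled at Weeks 1 and 2, before escalation, so those values in a 5 mg column were measured on 2.5 mg.

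Second, if a patient does not reach 5 mg, the column depends on which SAP section the programmer follows. Under 3.2.2 and 7.1.1, membership of the 2.5 mg and 5 mg columns is settled partly by a safety outcome after randomisation, and the 2.5 mg denominator is no longer the six patients who took that dose.

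**Working it through.** **Inputs.** Cohort of 8, randomised 3:1 (SAP 1.2); 84 planned daily doses (SAP 5.2); 5 mg for the last 10 of 12 weeks (SAP 1.2.5); final visit at Day 112 (SAP Table 1). The documents give no DLT or non-escalation rate, so that rate is an assumption, shown over a range.

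**The plan's own figures.** 8 × 3/4 = 6 active and 8 × 1/4 = 2 placebo. 8 cohorts × 8 = 64 patients. 12 − 2 = 10 weeks on 5 mg, or 84 − 14 = 70 days. All agree with the SAP.

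**Share of cohort 1 time on 2.5 mg, if all six escalate and complete.**

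- Planned treatment: 14/84 = 16.7%; in patient-days, 6 × 14 = 84 of 6 × 84 = 504.
- Time to Week 16: 14/112 = 12.5%.

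At a constant event rate over treatment, about 1 in 6 on-treatment events would carry the higher dose label. The share is larger if events cluster early.

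**Chance that the grouping conflict arises.** With probability p that an active patient does not reach 5 mg, and patients independent, the chance of at least one among six is 1 − (1 − p)^6.

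| Assumed p | At least one does not reach 5 mg | All six escalate |
|---|---|---|
| 5% | 26.5% | 73.5% |
| 10% | 46.9% | 53.1% |
| 20% | 73.8% | 26.2% |
| 33% | 91.0% | 9.0% |

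**What the table would show (assumed counts).** Scenario A: one patient has a DLT on 2.5 mg and stays there; no other events. Scenario B: as A, and in addition one escalated patient has an event only in Days 1-14 and another has a first event on 5 mg. Scenario C: all six escalate, with one patient having an event in each period.

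| Rule | A | B | C |
|---|---|---|---|
| Highest dose received (3.2.2, 7.1.1) | 2.5 mg 1/1; 5 mg 0/5 | 2.5 mg 1/1; 5 mg 2/5 (40%) | 5 mg 2/6 (33%); no 2.5 mg column |
| All cohort 1 active as 5 mg (3.1) | 5 mg 1/6 (17%) | 5 mg 3/6 (50%) | 5 mg 2/6 (33%) |
| Dose at onset (not planned) | 2.5 mg 1/6 (17%); 5 mg 0/5 | 2.5 mg 2/6 (33%); 5 mg 1/5 (20%) | 2.5 mg 1/6 (17%); 5 mg 1/6 (17%) |

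In Scenario C nobody is sorted by outcome, yet the 2.5 mg event still appears under 5 mg. In A and B the two existing rules give different tables from the same data.

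**The case against.** The strongest case for leaving the text alone has five parts.

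- **The rule is prespecified and the table is accurate for what it says.** Both documents classify safety by highest dose received. A reader might infer that the low-dose safety table is wrong by construction. The documents do not support that: as a count of patients by highest dose received it is correct, and it misleads only when read as incidence by dose.
- **Sorting by DLT is conditional.** It needs a patient who does not reach 5 mg, and it needs 3.2.2 and 7.1.1 to prevail over 3.1. A reader might also infer that a 2.5 mg column would hold only patients with a DLT. That does not follow: someone who stops study drug before Day 15 for an administrative or personal reason (SAP 1.2.3) also has 2.5 mg as highest dose, with or without an event.
- **3.1 and 3.2.1 can be read together.** 3.1 may be the specific label for cohort 1 and 3.2.1 the general principle. Using assignment for efficacy and dose received for safety is a legitimate choice. This is fair, but it does not settle 3.1 against 3.2.2 and 7.1.1, since 3.1 covers data presentations without limiting them to efficacy.
- **The scope is small.** If all eight cohorts enrol, the 84 patient-days are 84/(8 × 6 × 84) = 84/4,032 = 2.1% of planned active exposure in Part 1. Later cohorts stay on one dose.
- **The information is recoverable and decisions do not wait for it.** Events are listed by patient (SAP 7.1), the number escalated is reported (SAP 4.1), and the data safety monitoring board and the sponsor review data during Part 1. A reader might infer that dose selection is compromised; the documents do not show that.

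These limits stand. They do not change where escalated patients' early events are counted, or the missing single rule for a patient who does not escalate.

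**Conclusion.** The concern holds in a limited form. For every escalated cohort 1 patient, events on 2.5 mg are reported under 5 mg, and no planned summary shows them by dose at onset. This follows from the text alone and affects up to six patients for 14 days each: 17% of that cohort's planned treatment days. The 1-in-6 share of events additionally assumes a constant rate.

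For a patient who does not reach 5 mg, whether through a DLT or an early stop, the SAP gives conflicting groups. How likely that is depends on a rate the documents do not state; at assumed rates of 5% to 33% it is 26.5% to 91.0%. If 3.2.2 and 7.1.1 govern, the two low-dose columns are split partly on a safety outcome; if 3.1 governs, there is no 2.5 mg column. Because safety is a primary objective and the correction is cheap, it should be made before the Part 1 tables are run.

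**What to change.** 1. Reconcile SAP 3.1, 3.2.1, 3.2.2 and 7.1.1 into one grouping rule for cohort 1 active patients that says explicitly where a patient who never receives 5 mg is placed. Label the group 2.5 mg then 5 mg. Bring SAP 1.2.5 into line with the DLT exception in SAP 1.2.
2. Record any departure from Protocol 14.3.1 in SAP 2.4, which at present states that there are no changes.
3. Add one cohort 1 adverse event table by dose at onset. The 2.5 mg column covers all dosed active patients; the 5 mg column covers escalated patients from Day 15. Give patients at risk and patient-days in each: 84 and 420 (6 × 70) if all six escalate and complete; with one patient staying on 2.5 mg and completing, 5 × 14 + 84 = 154 and 5 × 70 = 350. State which column takes events with onset after the last dose.

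A single cohort 1 group mixes patients who did and did not receive 5 mg; the table by dose at onset is what separates the doses. The cost is SAP wording, one column label and one small table from onset dates already collected (Protocol 12.6). No clinical rule changes.
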